3.6 Acceptability Measures

Method acceptability will be assessed based on responses to questions about vaginal bleeding (at baseline) and other side effects, likes, and dislikes about the regimen at month 4, 8, and final visits.

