9 ASSESSMENT OF ACCEPTABILITY

The acceptability of a Sayana® Press injected every 4 months will be assessed and recorded on appropriate study CRFs at regularly scheduled visits (months 4, 8, and final). Acceptability questions will include questions such as acceptability of bleeding pattern and whether the participant would use the method in the future.

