Treatment will begin in the first 5 days of menses. A single MPA serum sample will be collected from all participants at baseline. All participants will be scheduled to receive re-injections at month 4 (approximately 17 weeks after treatment initiation) and month 8 (approximately 35 weeks after treatment initiation) and complete their planned follow-up at month 12 (approximately 53 weeks after treatment initiation). There will be a plus 7-day grace period for re-injections, but women who are up to 28 days late may continue treatment if they have a negative urine pregnancy test. Urine pregnancy testing will be performed at month 4, at study exit, at month 8 if the participant is more than 7 days late for her visit, and at any time during the study if clinically indicated. Participants will be evaluated for injection site reactions and asked to provide information on adverse events, prohibited concomitant medications and other contraceptive use, vaginal bleeding, and method acceptability at months 4, 8 and 12. Information on adverse events and use of any prohibited concomitant medications will be recorded if reported by participants at month 2 and 3 PK visits and at any unscheduled visits.

III. General Analytic Considerations

A. Study Size and Power

The sample size of 710 women receiving injections in the abdomen or upper thigh is expected to be sufficient to ensure that the difference between the estimated Pearl Index (pregnancies per 100 woman-years of use) and the corresponding upper 95% confidence bound does not exceed 1.0, so long as the observed Pearl Index is less than 0.75 and at least 80% of participants complete 12 months of follow-up. (The study has a 90% chance of achieving this precision target if the true (unobserved) pregnancy rate is no more than 0.5 per 100 women-years). In

addition, a cohort of 120 women (40 receiving injections in each the abdomen, upper thigh, and back of the upper arm) is sufficient to provide 85% power to detect 30% relative differences in PK parameters between injection sites, assuming the coefficient of variation is no more than 40% and using two-sided 0.05 level significance tests.

B. Data Source

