Data management (DM) plans are detailed in a separate study-specific document. Briefly, study center data are recorded on paper case report forms (CRFs) which are scanned by the study centers and entered into a clinical database management system at FHI 360. Data will be verified by study monitors and appraised for consistency by FHI 360 DM staff using both automated logical checks and manual review. A trained medical coder at FHI 360 will code all SAEs, AEs leading to product withdrawal, and AEs that are Grade 1 or higher ISRs using the Medical Dictionary for Regulatory Activities (MedDRA). Any adjudication of estimated dates of fertilization or other endpoint data will be performed following FHI 360 Standard Operating Procedures (SOPs). A central laboratory (PPD Development) will perform serum MPA testing, with results transferred to FHI 360 DM via password-protected Excel files. FHI 360 DM will create SAS datasets (version 9.4 or higher) containing lab and CRF data for use by biostatisticians conducting interim and final analyses.

C. Missing Data

It is anticipated that some event dates required for safety analyses may be incomplete. Decision rules for how and when to impute such incomplete date fields will be developed and documented by the medical monitor when reviewing study data and be documented in any study report produced. All other missing data will be ignored (i.e., treated as missing at random) unless patterns are identified through exploratory analysis which suggest the potential for biased assessments of efficacy, safety, PK, or acceptability. In the event such patterns are identified, rules for imputing data will be clearly described and justified in the study report.

D. Covariate Adjustment

The primary efficacy analysis will adjust for study center through stratification. Any other adjustments for covariates are addressed in the relevant sections below.

E. Test Size and Confidence Levels

Unless otherwise noted, all confidence intervals reported for the primary, secondary, and subgroup analyses will be computed at the 95% coverage level, and all p-values will be assessed at the two-sided 0.05 significance level, with no adjustment for multiple testing.

IV. Randomization, Allocation Concealment, and Blinding

A. Randomization

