Answers to questions about bleeding pattern (such as type of bleeding, average cycle length, duration of flow, and amount of flow) will be summarized by study center, injection site, and overall at enrollment, months 4 and 8, and final visit using appropriate measures (i.e., means, standard deviations, medians, minima, and maxima for continuous variables, and numbers and percentages for categorical ones). Blood pressure and body weight will also be summarized by study center, injection site, and overall at enrollment, months 4 and 8, and final visit using means, standard deviations, medians, minima, and maxima. Changes from baseline in bleeding patterns, blood pressure, and body weight at month 4, month 8, and final visit will also be summarized using shift-tables.

C. Acceptability

Acceptability endpoints include responses to questions about perception of bleeding patterns (recorded at enrollment, months 4 and 8, and final visit) and other side effects, likes, and dislikes about the regimen (recorded only at final visit). Acceptability will be assessed using the Treated Population and Safety Analysis Set. These will be summarized for each relevant visit by

study center, injection site, and overall using frequencies and percentages. Changes in perception of bleeding patterns overtime will be summarized using shift-tables.

XI. Analysis of Exploratory Study Objective

Plans for analysis of the exploratory objective will be described in an appendix to this document.

XII. Additional Data Summaries

Any concomitant medications recorded at enrollment or during the study will be provided in a listing including at least the following information: participant number, actual injection site, generic name and dosage of medication, administration route, indication, days from enrollment to start date, and duration of use.

XIII. Sensitivity Analyses

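### SAP X.C takes side effects, likes and dislikes only at the final visit, whereas protocol 3.6 takes them at months 4, 8 and final, so their time course and the answers of women with no final visit are lost

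*SAP*

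**What the plan says.** SAP X.C defines two groups of acceptability endpoints with different schedules. One is "perception of bleeding patterns (recorded at enrollment, months 4 and 8, and final visit"). The other is "other side effects, likes, and dislikes about the regimen (recorded only at final visit"). The population is not restricted to completers: "Acceptability will be assessed using the Treated Population and Safety Analysis Set". Summaries are descriptive, by center, injection site and overall, with shift tables for bleeding perception only.

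The protocol gives a different schedule for the second group. Section 3.6 lists "other side effects, likes, and dislikes about the regimen at month 4, 8, and final visits". Section 9 says that acceptability "will be assessed and recorded on appropriate study CRFs at regularly scheduled visits (months 4, 8, and final"), and offers future use of the method as an example question. Section 10.9 plans summaries of bleeding perception and the other acceptability responses from enrollment, months 4 and 8, and the final visit. SAP section II still describes women being asked about "vaginal bleeding, and method acceptability at months 4, 8 and 12".

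On missing data, SAP III.C starts from this default: "All other missing data will be ignored (i.e., treated as missing at random"). It then makes an exception where exploratory analysis suggests possible bias, and names acceptability among the assessments concerned.

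**The concern.** Acceptability over 12 months of use is a secondary objective. A single reading at the end says nothing about whether side effects and dislikes fade, persist or build up across the three injection cycles, which is what three visits would show. Under SAP X.C only bleeding perception keeps a repeated measurement.

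A single reading also depends on who is there to give it. A woman who attends at month 4 or month 8 and is then lost would have given answers on side effects, likes and dislikes under the protocol schedule. Under the SAP she gives none on those items. Disliking the method is a plausible reason for not coming back, so ignoring her missing final answer is a weak default.

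Protocol 10.13 asks that departures from its analyses be documented with their reasons, in an amendment, the SAP or the study report. SAP X.C offers no reason. Its change log is silent too, although that log covers only changes after version 1.0 and would owe no entry if the wording was there from the start.

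**Working it through.** There is no planned figure to reproduce here. The check is a comparison of texts, followed by a bounding calculation.

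**Step 1: how direct is each conflict?**

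- Protocol 3.6 against SAP X.C: direct. Same items, different visits.
- Protocol 10.9 against SAP X.C: close to direct. It covers the acceptability responses other than bleeding perception and names the interim visits.
- Protocol 9 and SAP II against SAP X.C: inconsistent, but both speak of acceptability in general.
- Protocol 3.14.3.1, 3.14.3.2 and Table 2: these put acceptability at months 4 and 8 without listing items. Asking only about bleeding perception would satisfy them.
- The future-use question appears in protocol 9 and not in SAP X.C, so its schedule in the SAP is unstated.

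**Step 2: who has a final visit?** Table 2 footnote k and protocol 3.14.3.3 apply final-visit procedures at any early discontinuation. Sections 3.14.3.1 and 3.14.3.2 apply them to women more than 28 days late. Section 3.12.2 limits this to what is possible, and 3.14.10 foresees loss to follow-up. The women missed are therefore those who leave or are lost with no final visit, and not all early leavers.

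**Step 3: how much could that matter?** Inputs:

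- 750 women enrolled (protocol 3.1).
- 80% completion. This is the minimum in the sample-size statement (protocol 10.1, SAP III.A), given there for the 710 abdomen and thigh women and applied here to all 750 as an assumption. It gives 0.80 × 750 = 600 completers and 150 early leavers.
- f, the share of early leavers who have a final visit. The documents do not give it, so it runs from 0 to 1.
- Favourable rates on some item: 80% in completers, and 40% or 20% in leavers. All are assumptions. Leavers seen and not seen are taken to have the same rate.

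Formulas, with p_c and p_d the rates in completers and leavers:

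- Completers' share of respondents = 600 / (600 + 150f)
- Final-visit estimate = (600 p_c + 150 f p_d) / (600 + 150f)
- Value in all women = (600 p_c + 150 p_d) / 750, which is (480 + 60)/750 = 72.0% at p_d = 40% and (480 + 30)/750 = 68.0% at p_d = 20%

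| f | Respondents | Completers' share | Estimate, p_d = 40% (all women 72.0%) | Estimate, p_d = 20% (all women 68.0%) |
|---|---|---|---|---|
| 0 | 600 | 100% | 480/600 = 80.0% | 480/600 = 80.0% |
| 0.5 | 675 | 88.9% | 510/675 = 75.6% | 495/675 = 73.3% |
| 1 | 750 | 80.0% | 540/750 = 72.0% | 510/750 = 68.0% |

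The overstatement is 8.0, 3.6 and 0 points in the 40% case, and 12.0, 5.3 and 0 points in the 20% case. It vanishes when every early leaver has a final visit. Early discontinuation alone does not produce it.

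The loss of the time course needs no calculation: under SAP X.C these items have one time point instead of three.

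**The case against.** The strongest reply is that only one protocol sentence, in 3.6, flatly contradicts SAP X.C on likes and dislikes. Most of the other passages speak of acceptability in general, and bleeding perception at months 4 and 8 could satisfy them. The items are descriptive and untested, and the CRFs are not among the documents. If the CRFs asked these questions only at the final visit, rewording the SAP recovers nothing. All of that is fair. It lowers the stakes and shapes the fix, but it does not remove the conflict or supply the missing reason.

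A reader might infer four stronger things, which the documents do not support:

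- *That the acceptability result describes mainly women who stayed.* Leavers who attend a discontinuation visit answer the same questions, and bleeding perception is recorded at every regular visit.
- *That a woman lost after month 4 or 8 contributes nothing.* She contributes bleeding perception up to that visit. Where known, her reason for leaving is recorded (protocol 3.12.2, 4.4) and summarised (SAP VIII).
- *That missingness is ignored unconditionally.* SAP III.C makes an exception for suspected bias and names acceptability. The exception has no preset trigger, but it exists.
- *That these questions are the only planned record of common side effects.* Bleeding pattern, weight, blood pressure and injection site reactions are all summarised under SAP X.B. What goes unrecorded on the AE form is other non-serious complaints that do not lead to withdrawal, and that follows from the protocol's recording rule (Table 2 footnote f), not from SAP X.C.

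**Conclusion.** The point holds as a conflict between protocol and SAP on when a set of secondary, descriptive items is recorded. As written, the SAP discards the month 4 and month 8 answers on side effects, likes and dislikes. That loss of time course is certain if the SAP is followed.

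The selection effect is possible but of unknown size. It comes only from women with no final visit. It ranges from nil to 8 points under the 80%/40% illustration, and to 12 points under 80%/20%, with 80% completion. The upper ends require that no early leaver has a final visit, which runs against the protocol's stated procedure. The favourable rates are assumed, so these figures show scale and are not estimates. The primary efficacy analysis is not affected.

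**What to change.** Amend SAP X.C to the protocol schedule. Collect and summarise side effects, likes, dislikes and the future-use item at months 4, 8 and final, by injection site and center. Report the number of final-visit respondents by completion status (completed, early leaver with a final visit), alongside the number of women with no final visit, so that a reader can judge the selection directly. State in the SAP which items the CRF collects at each visit.

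If the CRF did not collect these items at months 4 and 8, record that as a deviation from the protocol with its reason, as protocol 10.13 requires, and state that the results for these items apply only to women with a final visit.

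I would not add a summary that carries the last answer forward and counts leavers as unwilling. It would mix 4-, 8- and 12-month exposure and impute an opinion, and the visit-by-visit tables do not need it.

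The cost is SAP wording and a few extra table columns, on visits that already exist.

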3.14.2 Enrollment Visit (Day 0)

The enrollment visit will take place during the first 5 days of menses. During this visit a urine pregnancy test will be performed and other eligibility criteria verified. Height, weight and BP measurements will be recorded. Vaginal bleeding information will be collected. Approximately 5 mL of blood for MPA testing will be collected before randomization.

After a participant is confirmed eligible and had all other enrollment procedures completed, the study site's randomization manager will open the next sequentially numbered randomization envelope from the appropriate stream of envelopes (PK cohort or non-PK cohort). Each participant will receive an injection of Sayana® Press in her assigned SC injection site, be monitored for at least 15 minutes for possible anaphylactic reactions and/or ISRs, and be scheduled to return to the clinic 4 months later for re-injection on study day 119 (17 weeks after enrollment) (participants who are unable to return precisely on study day 119 may have their re-injection scheduled to take place up to 7-days late, on or before study day 126). Participants in the PK cohort will be scheduled to return for additional blood draw visits at month 2 (study day 61) and month 3 (study day 91), allowing for a plus/minus 7-day grace period.

In summary, the following will be done during the enrollment visit:

- Urine pregnancy test performed
- Study eligibility confirmed and baseline data collected
- Coital frequency and condom use assessed
- Vaginal bleeding assessed
- BP, height, and weight measured

- Blood drawn for MPA assessment (MPA testing will only be done on specimens from participants in the main cohort if MPA is detected above the threshold defined in the Statistical Analysis Plan among baseline specimens from the PK cohort)
- Randomization completed
- Study drug administered and site of injection evaluated for possible ISRs
- Study visit schedule provided
- Appropriate CRFs completed

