4.2 Exclusion Criteria

Women will be excluded from this study if they meet any of the following criteria at enrollment:

- has a primary partner who has received a vasectomy or is otherwise sterile
- medical contraindications to depot medroxyprogesterone acetate (DMPA) per WHO medical eligibility criteria for contraceptive use [33]
- known HIV-infection (for her or a partner)
- diagnosis or treatment for an STI in the past month (for her or a partner), excluding recurrent herpes or condyloma
- received an injection of a progestin-only containing contraceptive (DMPA or norethisterone enanthate) in the past 12 months

- received an injection of a combined injectable contraceptive in the past 6 months
- known or suspected allergic reaction to DMPA
- used a levonorgestrel intrauterine system, NuvaRing, contraceptive patch, oral contraceptives or a contraceptive implant in the past 7 days (PK cohort only)
- Previous (within 1 month prior to enrollment), current or planned (in the next 12 months) use of an investigational drug, prohibited drug per protocol (see Section 5.3) or other drug which in the opinion of the investigator could complicate study findings
- has been pregnant in the past month
- is lactating
- plans to move to another location in the next 12 months
- has a social or medical condition which in the opinion of the investigator would make study participation unsafe, or interfere with adherence to protocol requirements.

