reports using condoms in the last 4 weeks but not at any other time since last injection, then only the last 4 weeks prior to the report visit will be excluded.

B. Pharmacokinetics Population and Analysis Set

The Pharmacokinetics (PK) Population is a subset of the Treated Population. The PK Population includes participants who agreed to serum MPA testing at 6 timepoints and were randomized into the PK cohort but excludes participants who did not contribute blood specimens for PK assessments, who had a baseline serum MPA concentration exceeding 0.05 ng/mL, or who required the use of more than one Sayana Press unit for their baseline injection (based on information provided on the injection CRF)³. The corresponding Pharmacokinetics Analysis Set will censor data collected after a participant receives an injection in an anatomical site which differs from the site used at enrollment and will exclude any MPA specimens collected during a time when a participant reports using a concomitant medication that may impact the PK of MPA as defined in the protocol. During the coding process, the medical monitor will define the length of the period of exclusion based on participants' use of concomitant medications on a medication-specific basis. The Analysis Set will also exclude MPA results from any blood samples collected after an injection where more than one Sayana Press unit was inserted into the participant's skin (i.e., if a participant had more than one unit inserted at her month 4 injection, then blood samples collected at months 8 and 12 would be excluded from the analysis set for that participant). PK analyses based on this analysis population will be performed according to the site of injection at enrollment, even if it was assigned or was received in error.

VI. Blind Review of Data

As indicated above, neither participants nor center staff will be blinded to injection sites. However, to the extent possible, decisions regarding additions or modifications to planned analyses, determination of exclusion from analysis populations or analysis sets, and rules for handling missing or incomplete data will be made by statisticians, clinicians, or other study staff who do not have access to individual treatment data. The actual level of blinding maintained when performing these activities will be described in the clinical study report.

VII. Analysis of Baseline Data

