Serum MPA concentrations that fall within defined sampling windows (see Appendix A) will be summarized by timepoint and injection site in the following ways: 1) graphically using box plots with whiskers extending to 5th and 95th percentiles, and 2) in tables using means, geometric means, quartiles, minima, maxima, standard deviations, and percent coefficients of variation. A listing of all MPA concentrations for each participant will be provided along with an indication of any that fall outside of defined sampling windows, or any excluded from the PK Analysis Set due to concomitant medication use, injection in an anatomical site different from the site used at enrollment, or insertion of multiple Sayana Press units at the time of injection. The listing will also include subject age and BMI at time of sampling.

Month 2, 3, and 4 data will be used to estimate the apparent half-life for each injection site based on mixed-effects log-linear models with random intercept and slope terms, under the assumption that the terminal phase of absorption begins by month 2.⁵ Unique variance components will be used for each injection site, and observations falling outside sampling windows will not be excluded. The estimated slope (*m*) for each injection site will be used to calculate the apparent half-life according to the following formula: $half-life = \ln(2)/(-m)$. Pharmacokinetics in the terminal phase will be compared across injection sites based on overall and, if significant at the 0.05 level, pairwise Wald-type tests of differences in fixed-effects intercepts and slopes. Differences in variance components (both within-and between-subject effects) will similarly be assessed using likelihood ratio-tests.

Accumulation of MPA concentrations at months 8 and 12 will be estimated for each injection site by calculating the geometric mean ratio (GMR) of trough concentrations at 8 or 12 months to the trough concentration at 4 months, using mixed-effects models to compute 95% CIs of each GMR (with unspecified covariance of log-transformed repeated measures). Any MPA concentrations that are measured more than 7 days past a participant's scheduled injection date (along with any future measurements) will be excluded from the above accumulation

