Two sensitivity analyses will be performed for the efficacy objective. A Pearl Index and exact 95% confidence interval will be computed per the primary analysis (section IX.B) but excluding any women who had protocol violations occurring at enrollment that warrant exclusion based on blind review. Another Pearl Index and exact 95% confidence interval will be computed per the primary analysis but excluding results from pregnancy tests taken at home and any time between a participant's last in-clinic pregnancy test and her exit from the study. This will assess the impact of final pregnancy tests completed at home in response to the COVID-19 pandemic.

Two sensitivity analyses will be performed for the PK objective. The first will assess the impact of baseline MPA on PK profiles and will include all participants (except for those who required the use of more than one Sayana Press unit) in the PK cohort who provide samples for MPA testing. This will be done in the following way: calculate the half-life (λ) for each injection site using the same method described in the secondary objective above but using the revised population; use that half-life to calculate the concentration at time t (CB_t) due to the baseline amount (C_0) using the following formula

$$CB_t = C_0 e^{-\lambda t};$$

then subtract that amount from the corresponding monthly concentrations for each participant. Summaries of trough concentrations will be provided using these modified values and population.

Secondly, a table summarizing trough concentrations and half-life will be provided for a population comprised of the PK Population plus any participants or samples excluded from the PK Population or Analysis Set based on injection issues (i.e., more than one unit inserted into skin).

XIV. Planned Interim Analyses

An independent DSMB will review interim data when approximately 250 participants have completed 18 weeks of follow-up. This single, pre-planned interim analysis is intended to inform a decision whether to stop or modify the study if the estimated probability of pregnancy pooled across all injection sites is greater than 2% in the first injection interval. Details are provided in a separate DSMB Operational Plan.

XV. MPA Testing of Baseline Serum Specimens

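### The baseline-MPA correction decays a pre-randomization residue with the half-life of the newly assigned injection site, so equal residues are corrected unequally by arm (a small effect, confined to one sensitivity summary)

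*SAP*

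**What the plan says.** The main PK analysis leaves out any woman "who had a baseline serum MPA concentration exceeding 0.05 ng/mL" (SAP V.B). SAP XIII brings these women back in a sensitivity analysis of the effect of baseline MPA. A half-life is calculated "for each injection site using the same method described in the secondary objective above but using the revised population". That half-life is used to project C_0 forward to each sampling time, and the instruction is "then subtract that amount from the corresponding monthly concentrations for each participant". The output is descriptive: "Summaries of trough concentrations will be provided using these modified values and population". Summaries in SAP X.A are by timepoint and injection site, so the corrected troughs will presumably be read side by side by site.

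The method referred to is the one in SAP X.A. It fits a log-linear mixed model to the month 2, 3 and 4 concentrations after the study injection, with a slope for each site, "under the assumption that the terminal phase of absorption begins by month 2".

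On the timing of C_0, Protocol 3.14.2 says: "Approximately 5 mL of blood for MPA testing will be collected before randomization". Protocol 4.2 excludes women who "received an injection of a progestin-only containing contraceptive (DMPA or norethisterone enanthate) in the past 12 months". Neither document states where any residual MPA would come from.

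**The concern.** C_0 exists before the injection site is assigned. The rate at which it disappears may vary between women, but randomization gives that rate the same distribution in all three arms. This is so whether the rate reflects release from an older depot or elimination from the circulation.

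The rate that SAP XIII applies is different in kind. It is estimated after the study injection, separately by assigned site, and the SAP itself describes it as a terminal absorption phase. Protocol 1.3.2.1 concludes that the PK of MPA may differ by site. Neither document gives a reason to carry a site-specific rate over to a residue that was there beforehand, and no common rate or range of rates is offered.

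The effect of injection site on trough concentration is part of a secondary objective (Protocol 2.2.2). A sensitivity analysis meant to show whether baseline MPA matters should not add an arm-dependent error to the troughs it re-summarizes.

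**Working it through.** **Benchmark.** The plan gives no figure for the correction. The only stated figure for site differences is 85% power for a 30% relative difference with 40 women per site, a 40% coefficient of variation (CV) and a two-sided 0.05 test (SAP III.A). On the log scale the SD is √ln(1 + 0.4²) = 0.385. A difference of ln 1.3 then gives power of 86.1% (normal) or 85.3% (noncentral t), so the figure reproduces. The standard error of a log ratio is 0.385 × √(2/40) = 0.086. The 95% confidence interval of a site ratio is therefore about a factor of exp(1.96 × 0.086) = 1.18 either way.

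**Inputs.** Half-lives come from the table in Protocol 1.3.2.1: thigh 80.9 days, abdomen 103.7, upper arm 247.3 (SD 534, N = 25), labelling study 43.2 (site not specified). They stand in for the trial's own estimates. Target days 119, 245 and 371 are from SAP Appendix A. C_0 = 0.1 ng/mL is one of the two levels named in SAP XV.

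**Formula.** CB_t = C_0 × exp(−λt) with λ = ln 2 / half-life, which equals C_0 × 0.5^(t/half-life). SAP XIII attaches the symbol λ to the half-life itself. Read literally, exp(−80.9 × 119) is zero and nothing is subtracted in any arm. That is a separate point, and the figures here use the evident intention.

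**Amount subtracted for C_0 = 0.1 ng/mL (ng/mL)**

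| Day | Thigh | Abdomen | Upper arm |
|---|---|---|---|
| 119 | 0.036 | 0.045 | 0.072 |
| 245 | 0.012 | 0.019 | 0.050 |
| 371 | 0.004 | 0.008 | 0.035 |

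For example, on day 119 in the thigh arm: 0.1 × 0.5^(119/80.9) = 0.1 × 0.361 = 0.036. For C_0 = 0.05 all entries halve.

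**Effect on the arm means at day 119.** Assume that 20% of women in each arm carry 0.1 ng/mL, that the trough from the study dose is 0.40 ng/mL in every arm (held equal to isolate the artefact), and that the residue's true half-life is 80.9 days. Uncorrected, every arm has the same mean, 0.40 + 0.2 × 0.0361 = 0.4072, and all ratios are 1. Corrected:

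- thigh: 0.40 + 0.2 × (0.0361 − 0.0361) = 0.4000
- abdomen: 0.40 + 0.2 × (0.0361 − 0.0451) = 0.3982, ratio to thigh about 0.995
- upper arm: 0.40 + 0.2 × (0.0361 − 0.0716) = 0.3929, ratio to thigh about 0.982

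With a true residue half-life of 43.2 or 103.7 days, the two ratios change by no more than 0.0003.

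**Later visits, same assumptions.** The upper-arm shortfall is 0.2 × 0.0381 / 0.40 = 1.9% at day 245 and 0.2 × 0.0312 / 0.40 = 1.6% at day 371. For the abdomen it is 0.2 × 0.0072 / 0.40 = 0.4% and 0.2 × 0.0042 / 0.40 = 0.2%.

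**Other scenarios at day 119 (shares and C_0 assumed; ratios to thigh).**

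| Share and C_0 | Abdomen | Upper arm |
|---|---|---|
| 20% at 0.05 | 0.998 | 0.991 |
| 20% at 0.1 | 0.995 | 0.982 |
| 20% at 0.2 | 0.991 | 0.964 |
| 100% at 0.1 | 0.977 | 0.911 |

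**Direction.** Use the protocol's 3-month troughs as stand-ins and the 20% at 0.1 scenario. The abdomen/thigh ratio moves from 0.47/0.41 = 1.146 to 0.4682/0.41 = 1.142, so a real gap shrinks. The arm/abdomen ratio moves from 0.43/0.47 = 0.915 to 0.4229/0.4682 = 0.903, so a real gap widens.

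**The case against.** **If the sites were identical, there would be no systematic bias.** This stands. A reader might infer that the correction creates a false site difference, with the upper arm looking lower even when the sites behave alike. The documents do not support that. With identical pharmacokinetics the three half-lives estimate one quantity, and the subtractions differ only by estimation noise with no fixed direction. A systematic distortion needs half-lives that truly differ, and then it alters a real difference.

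**The large contrasts rest on one weak number.** This also stands. The upper-arm subtraction is about 2, 4 and 8 times the thigh subtraction only because of the 247.3-day mean with SD 534. The SAP derives half-life from a fixed-effect slope for each site, which is less exposed to a few nearly flat individual profiles. Protocol 1.3.2.1 also describes the upper-arm mean profile as closer to the abdominal data. If the trial's upper-arm half-life came out near 104 days, its ratio to thigh in the 20% scenario would be about 0.995, not 0.982.

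**Near-zero or undefined corrected troughs.** One might fear that over-subtraction ruins the geometric means. That would take residues of roughly 0.5 ng/mL, above every mean 3-month trough in the protocol's table (0.40 to 0.47). SAP XV names only 0.05 and 0.1 ng/mL as thresholds, and nothing in the documents suggests residues of that size.

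**A pooled slope also comes from the new depots.** True: a common rate is not thereby the right rate. But its error per unit of C_0 is the same in every arm, which is what a between-site reading needs.

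**The residue's source is unknown.** True, and calling it an earlier injection would be an inference; Protocol 1.3.1 notes that oral MPA exists. The argument needs only that C_0 predates randomization.

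**Conclusion.** The point holds, at low severity. SAP XIII ties the decay of a pre-randomization quantity to a post-randomization assignment, and no other section cures this. The artefact exists whenever the estimated site half-lives differ, which separate estimation makes practically certain.

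Its likely size is under about 2% of the mean trough. That rests on three assumptions: a 20% share of women at 0.1 ng/mL, a true trough of 0.40 ng/mL, and the protocol's earlier half-lives in place of the trial's own. The SAP XV percentages are triggers for further testing, not expected prevalences, so they do not establish the share. A distortion of about 9% (upper arm against thigh) would need every woman to carry 0.1 ng/mL. Either figure is well inside the 30% design difference, and 2% is small against a confidence interval factor of 1.18.

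It would be wrong to read this as a flaw in the trial's PK or efficacy conclusions. SAP XIII specifies no between-site test on the corrected values. The half-life, accumulation and site comparisons in SAP X.A and the Pearl Index do not use them.

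**What to change.** In SAP XIII, replace the site-specific half-life in the correction with one decay rate for C_0 in all three arms, for example the slope pooled over injection sites. Repeat the trough summaries with common bounding half-lives that span the values in Protocol 1.3.2.1: 43 and 104 days, with 247 days as an optional extreme. At day 119 these subtract 0.015, 0.045 and 0.072 ng/mL from every woman with C_0 = 0.1 ng/mL, whatever her arm, so the arm-dependent part of the correction disappears. Define λ as ln 2 / half-life in the same sentence.

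The cost is one sentence and two or three re-runs of the same code, with no new data. The downside is that a common rate remains an assumption about a residue of unknown source. The bounds make that visible.
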